8.5.2. Analysis of Time-to-Event Exploratory Endpoints

Time-to-event exploratory endpoints include:

- Time to antibodies normalization or negative status (anti-dsDNA antibody normalization, anti-C1q antibody negative status)
- Time to complement (C3, C4) no longer being low
- Time to relapse or proteinuric flare
- Time to SLE Flare Index of severe, moderate, or mild

The time-to-event exploratory endpoints will be analyzed using similar Kaplan-Meier and log-rank test methods as the main analysis of the time-to-event secondary efficacy endpoints. Similar censoring rules will be followed as for the time-to-event secondary efficacy endpoints (see Section 8.4.2).

No graphs will be produced for the time-to-event exploratory endpoints.

8.5.3. Analysis of Binary Exploratory Endpoints

Binary exploratory endpoints include:

- Proportion of patients achieving PRR with successful taper of prednisone or equivalent to ≤5 mg by Week 17
- Proportion of patients achieving PRR with no use of prednisone or equivalent during the 8 weeks prior to the renal response assessment

- Proportion of patients who meet CRR by the China Center for Drug Evaluation (CDE) of NMPA Technical Requirements (Appendix 4), which is achieved if both of the following conditions are met:
 - urine protein quantification <0.5 g/24 h or urine protein/creatinine ratio (UPCR)
 <0.5 g/g;
 - eGFR reduction ≤10% of baseline or eGFR ≥90 mL/min/1.73 m².
- Proportion of patients who meet PRR by the CDE Technical Requirements definition (Appendix 4), which is achieved when both of the following conditions are met:
 - partial renal response can be regarded if urine protein quantification reduction ≥ 50% of baseline and <3.5 g/24 h, or UPCR reduction ≥ 50% of baseline and <3.0 g/g;

and

- eGFR reduction ≤ 10% of baseline or eGFR ≥90 mL/min/1.73 m².
- Proportion of patients who achieve urine protein quantification <0.5 g/24 h or urine protein/creatinine ratio (UPCR) <0.5 g/g and eGFR reduction ≤20% of baseline or eGFR >60 mL/min/1.73 m².
- Proportion of patients who achieve urine protein quantification <0.5 g/24 h or urine protein/creatinine ratio (UPCR) <0.5 g/g and eGFR reduction ≤15% of baseline or eGFR ≥60 mL/min/1.73 m².
- Proportion of patients who develop doubling of Baseline serum creatinine, kidney failure (receiving dialysis or kidney transplantation), or death
- Proportion of patients with Baseline SLEDAI-2K, excluding renal components, ≥6 with at least a 4-point improvement
- Proportion of patients with relapse or proteinuric flare
- Proportion of patients with SLE Flare Index of severe, moderate, or mild

The binary exploratory endpoints will be analyzed using similar CMH methods as the main analysis of the primary estimand.

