2. OBJECTIVES

The overall study objectives are to evaluate the efficacy and safety of zetomipzomib in patients with active Class III or IV (with or without Class V; Class III/IV +/-V) LN and for those with pure Class V LN.

Specific efficacy, safety, and exploratory objectives are as follows:

Primary and Secondary Efficacy Objectives

The primary and secondary efficacy objectives are to evaluate zetomipzomib compared with placebo in patients with active Class III/IV +/-V LN on background MMF or equivalent, and corticosteroids based upon current guideline-driven standard of care. Patients with pure Class V LN on similar background therapy will also be evaluated as a subgroup.

Primary Safety Objective

The primary safety objective is to determine the safety and tolerability of zetomipzomib in patients with active LN on background standard of care, MMF or equivalent, and corticosteroids.

Exploratory Objectives

The exploratory objectives include the following, each on background standard of care therapy:

- To evaluate the speed of action of zetomipzomib compared with placebo
- To evaluate the clinical benefit of zetomipzomib compared with placebo
- To evaluate changes in serum levels of selected parameters in zetomipzomib compared with placebo
- To evaluate the efficacy of zetomipzomib compared with placebo on clinical lupus disease assessments
- To evaluate the efficacy of zetomipzomib compared with placebo on improving patient's quality of life
- To evaluate relapse in zetomipzomib compared with placebo
- To evaluate glucocorticoid-related AEs in zetomipzomib compared with placebo
- To evaluate renal histopathology and immunohistopathology (at selected sites based on feasibility)
- To evaluate biomarkers
- To evaluate the pharmacokinetics of zetomipzomib

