3.2.1.4. Treatment Failure

A patient experiencing one or more of the following criteria define treatment failure:

- Prednisone or equivalent* beyond that permitted (see Section 6.2.1.2 of the study protocol), to include:
 - >10 mg/day for ≥3 consecutive days or for ≥7 days in total during the 8 weeks prior to the renal assessment at
- MMF or equivalent* >2 g/day after Week 25
- Requiring rescue therapy (see Section 6.2.3 of the study protocol for details), as verified by the CEC

Statistical Analysis Plan, Version 1.0 Date Issued: 24Jul2024

• Use of prohibited medications (see Section 6.2.4 and Appendix 2 of the study protocol for details) or inappropriate use of the required concomitant medications (see Section 2.2.5 of the study protocol), as determined through manual data review by the CEC

• Discontinuation of zetomipzomib or placebo

Whenever possible, a complete disease activity assessment (eg, SLEDAI-2K, SLE flare index, PGA) and laboratory assessments (hematology, chemistry, urinalysis, anti-dsDNA, and C3 and C4) should be performed to document flare prior to initiating treatment that results in a treatment failure designation. Treatment failure does not necessarily require discontinuation of zetomipzomib or placebo. See Section 8.1.2 of the study protocol for individual patient stopping rules.

Treatment failure will be adjudicated in blinded fashion by the CEC. Details of this process will be provided in the separate CEC Charter.

*See Appendix 2 for dose conversion of other corticosteroid medications to prednisone equivalent and conversion of mycophenolic acid (MPA) and mycophenolate sodium (MPS) to MMF equivalent.

3.2.1.5. **Relapse**

Relapse is defined as loss of CRR at 2 consecutive time points

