3.2.1.6. Proteinuric flare

Proteinuric flare is defined as doubling from lowest baseline or post-baseline UPCR and at 2 consecutive time points:

- If patient achieved CRR, then doubled UPCR value must be >1 at 2 consecutive time points to be considered a flare
- If patient achieved PRR, then doubled UPCR value must be >2 at 2 consecutive time points to be considered a flare

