4. GENERAL STATISTICAL CONSIDERATIONS

This section presents general rules for the derivation and reporting of study data. If a subsequent section related to a specific derivation or analysis differs from this general guidance, the subsequent section takes precedence.

Unless specified otherwise, all study data will be summarized using descriptive statistics. Descriptive statistics for continuous data include number of patients (n), mean, standard deviation (SD), median, quartiles, minimum, and maximum. Categorical data will be described using frequency counts and percentages in each category.

Mean, median, and quartiles will be displayed to one level of precision greater than the data as originally collected. Standard deviation will be displayed to two levels of precision greater than the original data. For the summary statistics of all numerical variables, unless otherwise specified, minimum and maximum will be displayed to the same level of precision as the original data.

When count data are presented, the percentage will be suppressed when the count is zero to draw attention to the non-zero counts. A row denoted "Missing" will be included in count tabulations where specified on the shells to account for missing values. Unless otherwise specified, the denominator for all percentages will be the number of patients in that treatment group within the analysis set of interest. Percentages will be presented to one decimal place except for the display of 100% frequency which will be displayed as 'XX (100)'.

P-values ≥0.001 will be presented to 4 decimal places as "0.xxxx". P-values <0.001 will be presented as "<0.001". P-values >0.999 will be presented as ">0.999". Confidence intervals (CIs) will be displayed to one level of precision greater than the data as collected.

Treatment groups will be labeled as "Zetomipzomib 60 mg", "Zetomipzomib 30 mg", and "Placebo". In general, all tables and figures will be presented by treatment group. All study data will be presented in by-patient data listings sorted by treatment group, patient ID, and assessment date/time.

"No patients qualify for this table" will be presented when there are no data available to report in a given table. A similar note will be presented for empty listings and figures.

For all other parameters, the baseline value will be defined as the last non-missing evaluation prior to the first dose of study treatment (zetomipzomib or placebo), unless otherwise specified.

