8.5. Exploratory Endpoints

All exploratory efficacy endpoints will be analyzed for the ITT Population (Class III/IV +/- V). A subset of exploratory endpoints will be analyzed for the pure Class V LN patients as described in Section 8.5.3.

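### Relapse or proteinuric flare is compared over all randomized Class III/IV +/- V patients although only responders are clearly able to have the event, so at equal durability the arm with more complete responders shows more relapses

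*SAP*

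**What the plan says.** One stated exploratory objective is "To evaluate relapse in zetomipzomib compared with placebo" (SAP section 2). Two endpoints serve it: "Proportion of patients with relapse or proteinuric flare" (SAP 8.5.3) and "Time to relapse or proteinuric flare" (SAP 8.5.2).

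The definitions tie the event to response. SAP 3.2.1.5: "Relapse is defined as loss of CRR at 2 consecutive time points". SAP 3.2.1.6 defines flare as a doubling from the lowest UPCR, with a threshold of >1 for patients who reached CRR. For the others it says "If patient achieved PRR, then doubled UPCR value must be >2 at 2 consecutive time points to be considered a flare". No threshold is given for a patient with neither response.

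The analysis set is not tied to response. SAP 8.5: "All exploratory efficacy endpoints will be analyzed for the ITT Population (Class III/IV +/- V"). SAP section 4 sets the default: "the denominator for all percentages will be the number of patients in that treatment group within the analysis set of interest". For the test, SAP 8.5.3 says "The binary exploratory endpoints will be analyzed using similar CMH methods as the main analysis of the primary estimand". The time version uses Kaplan-Meier and log-rank methods with censoring rules similar to those of SAP 8.4.2, under which a patient who completes treatment without the event is censored the day after Week 53. Neither document restricts these analyses to responders, starts the clock at first response, or defines a sustained-response endpoint.

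**The concern.** A patient who never reaches CRR cannot lose it. In an all-randomized comparison that patient is recorded without relapse, in the same cell as a patient who reached CRR and kept it. The worst course and the best course are scored alike. If the drug raises the CRR rate, it raises the number of patients who can relapse, and the table can point against the drug because the drug works. The log-rank version has the same problem: never-responders who complete treatment stay in the risk set throughout and are censored event-free.

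At stake is how one exploratory objective is read, in a Phase 2b trial whose results are meant to inform the Phase 3 dose. The primary test is not involved.

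**Working it through.** **Inputs.** From SAP 4.2: CRR 40% on drug and 20% on placebo, 83 patients per group, two-sided alpha 0.05, pooled-variance binomial test. Assumed, because neither document gives them: r, the event risk among patients who reach CRR, and f, the flare rate among patients who do not. The Week 37 CRR rates stand in for the proportion who ever reach CRR.

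**Check of the plan's own figure.** With p̄ the mean of the two rates, power = Φ{[|p₁ − p₂|√n − 1.96√(2p̄(1 − p̄))] / √(p₁(1 − p₁) + p₂(1 − p₂))}. For 0.40 vs 0.20 and n = 83: (1.822 − 1.270)/0.632 = 0.873, so power is 80.9%. The SAP states 80%. The same method needs 82 per group, against 83 planned.

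**Relapse component alone, equal durability.** Expected proportion = P(CRR) × r. The next-to-last column applies the power formula; the last enumerates the same pooled test exactly.

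| r | Drug vs placebo | Expected patients of 83 | Chance of nominal excess on drug | Exact |
|---|---|---|---|---|
| 10% | 4% vs 2% | 3.3 vs 1.7 | 11% | 10% |
| 20% | 8% vs 4% | 6.6 vs 3.3 | 19% | 17% |
| 30% | 12% vs 6% | 10.0 vs 5.0 | 27% | 27% |

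**Break-even.** The proportions are equal when 0.40 × r(drug) = 0.20 × r(placebo), that is, at a risk ratio of 0.50 among responders. With placebo r = 30%, the drug-minus-placebo difference is +6.0 points at a ratio of 1.0, +3.0 at 0.75, 0 at 0.50 and −3.0 at 0.25.

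**The composite as listed.** With r and f equal in both arms, the difference is (0.40r + 0.60f) − (0.20r + 0.80f) = 0.20 × (r − f). For r = 30%:

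| f | Drug vs placebo | Difference |
|---|---|---|
| 0% | 12% vs 6% | +6 points |
| 10% | 18% vs 14% | +4 |
| 20% | 24% vs 22% | +2 |
| 30% | 30% vs 30% | 0 |
| 40% | 36% vs 38% | −2 |

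**How large might f be?** Protocol 1.1.2 says that about 50% of patients improve on standard therapy and about 25% reach CRR. If the remaining 25% stand in for PRR without CRR (an assumption), they are 0.25/0.75 = one third of non-CRR patients. If only they can flare, f = 30% would need 0.30/(1/3) = 90% of them to flare. A 30% flare risk among them gives f = 10% and a +4 point excess. If patients with neither response can also flare, f could be higher.

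**Sustained response over all randomized patients.** Proportion = P(CRR) × (1 − r). At r = 10, 20 and 30% this is 36 vs 18%, 32 vs 16% and 28 vs 14%, with power 75, 68 and 60%.

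**The case against.** The strongest reply is that the listed endpoint is a composite. A patient with PRR only can flare, so the relapse-only rates above are not what the SAP's table would show, and the excess can vanish or reverse. That stands, and it limits the size of the point. It does not remove it, because on the thresholds given, flare also follows a response.

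Second, a reader might infer that an effective drug is bound to show more relapses. The documents do not support that. They give no relapse or flare rate, and equal durability is an assumption. If the drug more than halves relapse risk among responders, it shows fewer relapses even over all randomized patients.

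Third, the SAP does not state outright that never-responders count as event-free. That follows from the definitions and the default denominator. The CMH method is borrowed from the primary estimand, which gives treatment failures and missing data the unfavourable result. How that carries over to an unfavourable event is not stated. Read one way, failures become events; read literally as not achieving the endpoint, a patient rescued for a disease flare is scored as having no event. This is a gap to close, not a defence.

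Fourth, a reader might infer that a sustained-response count answers the relapse question. It does not. At equal durability the true relapse contrast is nil, yet sustained response reads 28 vs 14%. It can also hide harm: if 60% of drug responders and 30% of placebo responders relapse, it reads 0.40 × 0.40 = 16% vs 0.20 × 0.70 = 14%, still in favour of the drug.

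Fifth, CRR at Week 53 is already a key secondary endpoint, and time to death or renal-related events already includes proteinuric flare. Both help. Neither shows whether a response once reached was kept.

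**Conclusion.** The point holds in a limited form. As written, the all-randomized comparison mixes the chance of responding with the chance of losing the response. At the SAP's 40% vs 20% and equal durability, the relapse component doubles on drug, with an 11 to 27% chance of nominal significance against it for r of 10 to 30%. The drug must halve relapse risk among responders to look equal on that component. For the composite, the excess is 0.20 × (r − f), which may be positive, zero or negative.

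These sizes rest on assumed r and f, on both being equal across arms, and on Week 37 CRR rates standing in for ever reaching CRR. Priority is low: the endpoint is exploratory and outside the multiplicity procedure, SAP 8.1 treats such p-values as nominal, and the primary conclusion does not depend on it.

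**What to change.** 1. Add an analysis of sustained response in the Class III/IV +/- V ITT population: CRR reached by Week 37 and kept through Week 53 without relapse or flare. Never-responders, treatment failures and patients with missing data count as not sustained. Use the same CMH method and describe the result as net benefit, not as a pure relapse comparison. The Week 37 limit prevents a first CRR at Week 53 from counting as sustained with no follow-up.
2. Report relapse or flare among patients who reached CRR, and flare among PRR-only patients, as descriptive counts by arm without p-values. These groups are formed after randomization.
3. Do not use the ITT CMH and log-rank p-values for relapse or flare as between-arm evidence.
4. State in the SAP whether a patient with neither response can have a flare, which visits count as time points, and how treatment failure and missing data are scored for an unfavourable event.

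Cost: one added exploratory table, one descriptive table, a few sentences in SAP 3.2.1 and 8.5, and an entry in SAP section 13. No new data are collected, and the endpoints listed in protocol 2.2.3 remain. The drawback is that sustained response mixes attaining and keeping a response, and could favour the drug even when its responders relapse more often, so it must be read beside the descriptive counts.

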8.2.2. Primary Analysis

The primary analysis of the primary estimand will be conducted when all Class III/IV+/- V LN patients in the ITT Population reach (or would have reached) Week 37. Patients who experience an intercurrent event (IE) as specified in Table 4 above prior to the Week 37 visit will be considered non-responders (ie, will be imputed as not achieving CRR) by using the composite IE strategy. Patients with missing CRR assessment at Week 37 due to any other reason will also be considered non-responders through imputation in the missing data strategy.

The proportion of patients achieving CRR at Week 37 will be compared between zetomipzomib and placebo (separately for each of the two dose groups and the combined dose groups vs. pooled placebo) using the CMH test at 2-sided 5% level of significance, stratified by the randomization stratification factors specified in Section 3.5. The following statistics will be presented:

- Number and proportion of patients achieving CRR
- Weighted difference in CRR proportions
- Odds ratio and associated 2-sided 95% CI
- p-value for each pairwise comparison between zetomipzomib and placebo

A bar graph showing the proportion of patients achieving CRR by treatment group with the weighted treatment difference and CMH p-value will be produced.

The CMH assumption of homogeneous treatment effect across strata will be tested using the Breslow-Day test. A significant Breslow-Day test (p-value <0.05) indicates that the treatment effect is not homogeneous across strata. Unstratified chi-square methods may also be used to analyze the primary estimand.

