13. CHANGES IN THE PLANNED ANALYSIS

- Analysis of opportunistic infections has been added in the SAP, Section 9.1.6.
- In the Protocol Section 10.6, jump to placebo and tipping point imputation analyses are mentioned as a method for dealing with missing data in general. However, in the SAP, we have removed these analyses for non-key secondary endpoints.
- Respiratory rate has been added to this SAP because it was inadvertently omitted from the Protocol, but was routinely collected during conduct of the study.
- Clarification that "Time to UPCR ≤0.5" is considered a secondary efficacy study endpoint, as this is mentioned as a 'variable' in Protocol Section 10.6: "For time-to-event variables (eg, time to CRR, time to PRR, and time to UPCR ≤0.5), the Kaplan Meier method...". This has been added to Table 1 in the SAP.
- The number of sites and countries has been updated in the SAP to "Approximately 214 sites from ~21 countries worldwide are planned to participate in this study" which differs from the number mentioned in the Protocol and is more accurate.
- Intercurrent events as defined in the Protocol (Table 6) were redefined and provided with clear labels in Section 8.2.1, for the purpose of the SAP. For example, non-responder events were combined under Treatment Failure (by definition) and Death was added.
- A Tertiary Estimand has been added to this SAP (for the PP Population) compared with the Protocol which called the analysis with the PP Population a 'supportive' analysis.
- Per Protocol, Section 10.6.1.1 states "For patients whose CRR at Week 37 cannot be adequately determined (including missing data, early study discontinuation, or lost to follow-up), their CRR will be imputed using an NRI approach.". In the SAP, Section 8.2.1, early study discontinuation, or lost to follow-up are being managed using the Estimand framework, see SAP, Table 5.

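### SAP 8.5.3 has no direction-specific rule for intercurrent events and incomplete follow-up on adverse binary endpoints, so early leavers, and on one reading failures and deaths, count as event-free

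*SAP*

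**What the plan says.** SAP Section 8.5.3 puts favourable responses (PRR with steroid taper, the CDE response definitions) and adverse outcomes in one list. The adverse ones are "Proportion of patients who develop doubling of Baseline serum creatinine, kidney failure (receiving dialysis or kidney transplantation), or death", relapse or proteinuric flare, and "Proportion of patients with SLE Flare Index of severe, moderate, or mild". One sentence covers them all: "The binary exploratory endpoints will be analyzed using similar CMH methods as the main analysis of the primary estimand". The section gives no assessment window for the adverse endpoints and no rule for intercurrent events or incomplete follow-up. Section 8.4.3 closes with an equivalent sentence for the binary secondary endpoints, which are all favourable.

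The analysis referred to is in Section 8.2.2. There, "Patients who experience an intercurrent event (IE) as specified in Table 4 above prior to the Week 37 visit will be considered non-responders", and "Patients with missing CRR assessment at Week 37 due to any other reason will also be considered non-responders through imputation". Table 4 names three intercurrent events: adjudicated treatment failure (which includes rescue therapy and stopping study drug), leaving the study, and death. Section 13 confirms that "non-responder events were combined under Treatment Failure (by definition) and Death was added".

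Two general rules in SAP Section 4 also matter. Percentages use every patient in the arm as denominator unless stated otherwise, and no imputation is planned beyond what the SAP sets out.

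**The concern.** For CRR, scoring failures, leavers and deaths as not achieved is conservative. For an endpoint where achieving means harm, the same score means no event. Some of the endpoint's own events also trigger the rule. Protocol 8.1.2 lists starting dialysis or receiving a kidney transplant among the reasons for stopping study drug, and stopping study drug is treatment failure in Table 4. Protocol 6.2.3 says that patients rescued for flare should stop study drug. Death is an intercurrent event in its own right.

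At stake is whether these tables show the event rates that occurred, and whether the comparison is distorted when more patients leave or fail in one arm than in another.

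**Working it through.** The documents state no rate, power or sample size for these endpoints, so there is no planned figure to reproduce. The check is what the text implies, followed by an illustration.

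**Readings of the 8.5.3 sentence**

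- **A. Composite handling and NRI carry over.** Treatment failures, early leavers and deaths become not achieved, that is event-free. A death would not count on an endpoint that names death as an event.
- **B. Only the CMH test carries over.** Observed events in patients who failed or stopped drug count, and so do deaths. Early leavers with no observed event stay in the full denominator with nothing imputed, so they count as event-free.
- **C. Non-responder is taken to mean the bad outcome.** Failures and leavers would count as events.

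The text does not choose. Early leavers without an observed event are event-free under A and B. Failures with an observed event, and deaths, are event-free only under A.

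**Illustration (all inputs assumed, except 83 patients per arm from SAP 4.2)**

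Let f be the share with an intercurrent event or early exit, p0 the event risk without one and p1 the risk with one.

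- True rate = (1 − f) × p0 + f × p1
- Rate reported under A = (1 − f) × p0

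Take p0 = 5%, p1 = 20%, f = 30% active and 15% placebo.

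- Active: true 0.70 × 5% + 0.30 × 20% = 3.5% + 6.0% = 9.5%; reported 3.5%.
- Placebo: true 0.85 × 5% + 0.15 × 20% = 4.25% + 3.0% = 7.25%; reported 4.25%.
- Difference, active minus placebo: true +2.25 points; reported −0.75 points. The sign reverses.
- Events lost: 83 × 6.0% = 5.0 active; 83 × 3.0% = 2.5 placebo.

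Other inputs:

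- p1 = 40%, same f: true 15.5% and 10.25% (+5.25 points); reported still 3.5% and 4.25% (−0.75).
- p0 = p1 = 20%, same f: true 20% in both arms; reported 14% and 17%, a false 3-point advantage.
- p0 = 5%, p1 = 20%, f = 15% in both arms: 7.25% is reported as 4.25% in both. Rates are understated, but no false difference appears.
- Over p0 of 5% to 20%, p1 of 5% to 50% and f of 15% to 30%, the loss is 0.6 to 12.4 events per arm (83 × 0.15 × 5% to 83 × 0.30 × 50%).

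**Under reading B** only events that go unobserved after study exit are lost. If s is the share of events in the f group lost this way, equal in both arms, the reported rate is the true rate − s × f × p1. In the first example that is 9.5% − 6s points and 7.25% − 3s points, so the difference is 2.25 − 3s points. It shrinks as s rises and changes sign only above s = 0.75. The bias is in the same direction as under A, but smaller.

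**The case against.** The strongest reply is that 8.5.3 names only CMH methods. Where the SAP means to carry handling rules over, it says so: 8.2.4 names NRI for subgroups, and 8.3 states that intercurrent events are assessed through the time point of interest. The non-responder rule is written for CRR at Week 37, and Protocol 10.6 applies NRI only where appropriate. Scoring a death as event-free on an endpoint that counts death is self-contradictory, so reading A is an unlikely intention. Under reading B the result is an ordinary crude proportion, the same kind that SAP 9.1 uses for adverse events. Patients who stop drug are encouraged to stay through end of study.

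Most of this stands. A reader might infer that the SAP prescribes event-free scoring for failures and deaths. It does not; that is one reading of an incomplete sentence. It is still a natural reading, because 8.4.3 uses an equivalent sentence for responder endpoints that have no other intercurrent-event or missing-data rule. Reading B limits the problem without removing it.

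A reader might also infer that this is the trial's only hard renal outcome. That is not supported. SAP 3.2.1.7 and 8.4.2 plan a secondary time-to-event endpoint covering death, creatinine doubling and kidney failure, with proteinuric flare added. Relapse or proteinuric flare and SLE flare have time-to-event analyses in 8.5.2, and deaths are tabulated under 9.1.11. What can be said is that the 8.5.3 composite is the only one limited to hard outcomes, and it has no time-to-event version of its own.

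**Conclusion.** The gap is real. Section 8.5.3 ties adverse endpoints to a responder analysis and gives no rule suited to their direction. Full carry-over contradicts the endpoint's own definition. Carrying over the test alone still counts early leavers without an observed event as event-free, which understates rates and can bias the comparison when exit differs by arm.

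The size cannot be derived from the documents. The figures above rest on assumed event and exit rates, and the sign reversal needs both unequal exit and a higher event risk among those affected. Nothing in the documents shows that either will occur.

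The endpoints are exploratory and outside type I error control, so the primary result and the sample size are untouched. This is a cheap improvement, not a flaw in the main analysis.

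**What to change.** In SAP 8.5.3, separate the adverse-direction endpoints from the favourable ones and state for the adverse group that:

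- the composite and NRI responder rules do not apply;
- every observed event through Week 53 counts, regardless of treatment failure or drug discontinuation;
- death counts as an event where it is a component, overriding for that endpoint the 8.4.2 rule that censors patients who die at their last UPCR assessment;
- the Week 53 proportion is estimated by Kaplan-Meier, or by cumulative incidence with death as a competing risk for the flare endpoints, with a comparison stratified by the randomization factors.

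Keep CMH with non-responder handling for endpoints where achieving is favourable. Kaplan-Meier assumes that leavers have the same later risk as those who stay, so a worst-case count for leavers is a reasonable sensitivity analysis.

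The cost is a few SAP sentences and minor programming. The planned time-to-event code can be adapted, but not reused unchanged, because it would censor deaths.
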